### **1. Description of the trial**

A two-arm parallel-group feasibility RCT with nested process evaluation to assess whether a full scale RCT is feasible and acceptable to participants. 72 parent/caregiver participants will be recruited via community pathways and randomised using a minimisation approach to either (i) Being a Parent-Enjoying Family Life (BAP-EFL) or (ii) standard Empowering Parents Empowering Communities- Being a Parent (EPEC-BAP), an active control group. A mixed-methods process evaluation incorporating quantitative data collected on attendance and fidelity and qualitative data from written feedback and semi-structured interviews with a subgroup of participants (n=24) will be carried out. No health economic evaluation will be undertaken at this feasibility stage.

This analysis plan should be read as a supplement to trial protocol, as such only a summary description of the trial design (See figure 1), research objectives, measures and sample size will be repeated here. For a detailed description of trial design and methods, see Being a Parent-Enjoying Family Life study protocol v5. 279116.

#### **1.1 Principal research objectives to be addressed**

The aim of this study is to examine the feasibility of trial methods and treatment acceptability to inform the planning and conduct of a definitive randomised controlled trial of BaP-Enjoying Family Life. The specific objectives are:

1. To assess (a) the primary feasibility parameters for participant recruitment and retention and (b) secondary parameters for BaP-Enjoying Family Life acceptability and fidelity.
2. To examine the acceptability of proposed trial methods, including randomisation.
3. To investigate the influence of participant and service factors on trial methods, intervention acceptability and fidelity, including in-depth qualitative analysis of interviews from a sub-group of participants to develop a fine grain understanding of parents/caregivers' subjective experience of trial and intervention procedures.
4. To obtain variance estimates for parents/caregiver and child outcomes for future sample size calculations.

#### **1.2 Progression to a full trial**

Progression from feasibility to a future definitive RCT is based on the criteria in Table 1. A traffic light system will be used with thresholds for each feasibility criteria of green, amber and red. Rating (a) is green and indicates progression to full trial is feasible; rating (b) is amber and indicates progress should be considered if improvements derived from feasibility findings are possible, and rating (c) do not progress before further testing.

**Figure 1. Trial design flow diagram**

[figure not shown]

Table 1. Primary and secondary feasibility progression parameters to pre-define whether the trial should progress to a definitive clinical trial.

| Parameter                |  |   |
|---------------------------------|--|---|
| Primary Progression Parameter   | Time 2 participant retention rate is sufficient for a fully powered definitive RCT                   | 
 
a. Time 2 retention at >65%
 
b. Time 2 retention at 45-65%
 
c. Time 2 retention rate at <45%
 
  |
| Primary progression parameter   | Trial participants who meet SAPAS criteria are identified at a sufficient rate for a definitive RCT. | 
 
a. > 60% of participants who complete informed consent will meet SAPAS criteria
 
b. 33%-60% of participants who complete informed consent will meet SAPAS criteria
 
c. < 33% of participants who complete informed consent will meet SAPAS criteria.
 
  |
| Secondary progression parameter | Trial participants are recruited at a sufficient rate required for a definitive RCT                  | 
 
a. 50-72 participants are randomised as planned
 
b. Between 25-50 participants are randomised
 
c. Less than 24 participants are randomised
 
  |
| Secondary progression parameter | BaP-Enjoying Family Life intervention is acceptable to parents/caregivers                            | 
 
a. At least 75% of parents rate BaP-Enjoying Family Life with a total TARs score of <math>\geq 27</math>
 
b. 55-74% of parents rate BaP-Enjoying Family Life with a total TARS score of <math>\geq 27</math>
 
c. <55% of parents rate BaP-Enjoying Family Life with a total TARs score of <math>\geq 27</math>
 
 |
| Secondary progression parameter | BaP-Enjoying Family Life & EPEC-Being a Parent Fidelity will be reached                              | 
 
a. 80% or more – Good Fidelity
 
b. 60-80% - Fair fidelity, deviation from the manual that may require further training and/or supervisory support
 
c. >60% - Significant deviation from manual, fidelity not reached
 
   |

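### The recruitment progression criterion is worded as a rate but banded on total numbers with no time base in the SAP, so slow or extended recruitment to 50 could rate green

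*SAP*

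**What the plan says.** SAP Section 1.2 gives every feasibility criterion a green, amber or red rating. Green means that a full trial is feasible, amber that progression should be considered if improvements can be made, and red that further testing comes first. Section 3.1 says the feasibility outcomes are judged against these parameters, so Table 1 is the operative rule.

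The recruitment row of Table 1 is labelled a secondary progression parameter and reads "Trial participants are recruited at a sufficient rate required for a definitive RCT". Its bands are:

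- green: "50-72 participants are randomised as planned"
- amber: "Between 25-50 participants are randomised"
- red: "Less than 24 participants are randomised"

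The target is in Section 1: "72 parent/caregiver participants will be recruited via community pathways". No recruitment period accompanies it.

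Objective 1 in Section 1.1 refers to "the primary feasibility parameters for participant recruitment and retention" and, separately, to "secondary parameters for BaP-Enjoying Family Life acceptability and fidelity". In Table 1 the two primary rows are Time 2 retention and a SAPAS row: "Trial participants who meet SAPAS criteria are identified at a sufficient rate for a definitive RCT".

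**The concern.** Whether a definitive trial can recruit depends on how many participants it randomises per unit of time from a given catchment. A total without a closing date does not measure that. Read as it stands, the row turns green when the 50th parent is randomised, and a longer recruitment period could by itself move an amber result to green. The total would then be carried forward as evidence of feasibility while saying nothing about pace.

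Two smaller faults sit in the same row. The bands are neither exclusive nor exhaustive, so two possible results have no unique rating. The row's label also disagrees with objective 1.

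**Working it through.** **The plan's own figure.** The recruitment row contains no derived figure to reproduce. The only sample-size figure in the SAP (Section 1.4) is a half-width of ±10.7 percentage points for a 70% follow-up rate with n = 72. The usual formula gives 1.96 × √(0.70 × 0.30 / 72) = 10.59 points, and 10.66 points with n − 1 = 71, which rounds to 10.7. It reproduces, but it concerns retention and has no bearing on this point.

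**Step 1: is there a time base anywhere in the SAP?**

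| Place in the SAP | What it gives | Time base for recruitment |
|---|---|---|
| Section 1 | target of 72 | none |
| Section 1.2, Table 1, recruitment row | totals randomised | none; *as planned* in green only, undefined |
| Section 1.3, recruitment and retention outcomes (i) and (ii) | numbers and percentages of parents interested, consenting or eligible | none |
| Section 3.1.2, Time points | assessment timing relative to randomisation and group dates | none |

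**Step 2: could the phrase in the green band supply a time limit?** Suppose it means randomised by a planned date.

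- If 50 are reached only after that date, the result falls in amber, because amber runs up to 50.
- If 51 to 72 are reached only after that date, the result fails green for lateness, exceeds amber's upper limit and is not red. It fits no band.

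The phrase therefore does not work as a time limit unless amber and red carry the same condition.

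**Step 3: what range of pace does the green floor cover?** The SAP gives no recruitment period, so the periods T below are assumptions. Pace = 50 / T.

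| Assumed T (months) | 50 / T (per month) | Rating on the count alone |
|---|---|---|
| 6 | 8.33 | green |
| 12 | 4.17 | green |
| 18 | 2.78 | green |
| 24 | 2.08 | green |
| 36 | 1.39 | green |

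The fastest and slowest differ by 36 / 6 = 6-fold.

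**Step 4: does each count get exactly one rating?** Green is 50 to 72, amber is 25 to 50 and red is below 24. Checking each count from 22 to 52, all but two get a single rating:

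- 50 satisfies both green and amber.
- 24 satisfies none.

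**Step 5: the label.** Objective 1(a) names recruitment and retention as primary. Objective 1(b) names only acceptability and fidelity as secondary. Table 1 calls the row worded as recruitment secondary. Section 1.2 attaches the same meaning to green, amber and red for every criterion and gives no rule for combining primary and secondary ratings. As written, the label alters no rating.

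**The case against.** The strongest reply is that the SAP describes itself as a supplement to the protocol and repeats only a summary of the design. A recruitment window is commonly left to the protocol, and the green band may well point to one. The trial flow diagram is also not shown. This stands in part: the missing date is not itself a fault. A reader might infer that the trial recruits open-endedly or that an extension is intended, and the SAP says neither. What remains is that the decision rule fixed here does not invoke a date in amber or red and leaves the phrase in green undefined.

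Second, *rate* in this SAP need not mean per month. The retention and SAPAS rows use it for percentages, and 50 of 72 is 69% of the target. That is a fair reading of the word. It does not rescue the row's purpose, because the share of this trial's own target says nothing about the pace a definitive trial needs.

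Third, a reader might infer that objective 1(a) goes unanswered for recruitment. That is too strong. Section 1.3 reports identification, screening, eligibility, consent and randomisation, with reasons for non-participation, and this answers part of it. What is missing is the pace.

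Fourth, the SAPAS row could be the recruitment meant in objective 1(a), since eligibility among those consenting is listed under the recruitment and retention outcomes. That softens the mismatch but does not remove it: objective 1(b) still has no place for the row that Table 1 words as recruitment.

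**Conclusion.** The point holds in a limited form. The row is presented as a test of a sufficient recruitment rate, but the SAP bands it on totals with no time base. Unless a closing date in the protocol is applied, slow or extended recruitment to 50 rates green and gives no information on pace. For assumed periods of 6 to 36 months, that single rating covers 8.3 down to 1.4 per month.

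Those paces are illustrative. A reader might go on to calculate how many years a definitive trial would take; the documents do not support this, because they give no recruitment period, no definitive sample size and no statement that the later trial would use the same areas.

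The overlap at 50 and the gap at 24 are certain and rest on no assumption. The label mismatch is real, but it is a matter of wording. It does not show that any rating is wrong, or that the row must become primary.

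**What to change.** Amend the recruitment row of Table 1 in a single edit:

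1. Apply all three bands to the number randomised by the originally planned end of recruitment, with a cross-reference to the protocol for the date. Exclude later randomisations from this criterion only; they stay in every other analysis.
2. Add randomisations per month, overall and by borough, to the recruitment outcomes in Section 1.3 as the figure carried to the definitive trial.
3. Make the bands exclusive and exhaustive, for example green at 50 or more, amber at 25 to 49 and red at 24 or fewer. The sponsor may place 24 in amber instead, provided that it is in one band.
4. Reconcile the label: either reword objective 1 or relabel the row. Rewording is the smaller change, since it leaves the progression hierarchy alone.

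No new data are needed. Borough is on the interest form, and randomisation dates should be held because the assessment time points are defined from randomisation. The downside is that, if recruitment is extended, the rating will be less favourable than the final total suggests.

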# **3. Data analysis plan**

## **3.1. Feasibility outcomes, adherence outcomes and progression criteria**

Feasibility and adherence outcomes will be summarising using descriptive statistics: number, percentages and proportions, mean and standard deviation as appropriate. These outcomes will be presented overall and also separately by arm in the

CONSORT diagram. The outcomes will be evaluated against pre-specified feasibility parameters as above (page 5) . No inferential statistics will be carried out on these feasibility outcomes.

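### Table 1 prints the red fidelity band as above 60%, so good fidelity is also rated red and poor fidelity has no rating; the recruitment bands overlap at 50 and omit 24

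*SAP*

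**What the plan says.** Section 1.2 of the SAP bases progression on the criteria in Table 1. Green (a) means a full trial is feasible, amber (b) means progression is considered if improvements are possible, and red (c) is defined as "rating (c) do not progress before further testing". Section 3.1 applies the table: "The outcomes will be evaluated against pre-specified feasibility parameters as above". The same section rules out inferential statistics on these outcomes.

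In the fidelity row of Table 1, the green band starts at 80%, that value included, and is labelled good. The amber band is worded as "60-80% - Fair fidelity, deviation from the manual that may require further training and/or supervisory support". The red band, which ought to hold the lowest results, is printed as ">60% - Significant deviation from manual, fidelity not reached".

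In the recruitment row, the green band runs from 50 to 72 people randomised. The amber band is given as "Between 25-50 participants are randomised". For the red band the table has "Less than 24 participants are randomised".

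Section 2.3 gives the fidelity score as a total out of 80 for BaP-EFL groups and 72 for BaP groups, also reported as a percentage. Nothing elsewhere in the SAP restates or corrects these thresholds.

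**The concern.** A traffic-light rule works only if each possible result falls in exactly one band. The fidelity row fails this over almost its whole range. The red band covers the results that the row's own labels call good or fair, and it misses the results that its label describes. Read literally, an 85% result is both green and red, a 70% result is both amber and red, and a 40% result has no colour.

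The recruitment row fails at its edges: one count has two ratings and another has none.

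The stake is pre-specification. This is a feasibility trial, fidelity is named in its first objective, and the bands are the only decision rule for the feasibility outcomes. If the bands are repaired after fidelity and recruitment are known, the sponsor can no longer show that the thresholds were fixed in advance.

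**Working it through.** There is no sample size or power figure to reproduce here. The check assigns every possible result to the bands as printed and counts overlaps and gaps.

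**Inputs.** Fidelity bands from Table 1: green ≥80%, amber 60-80% (ends included), red >60%. Score ranges from section 2.3: whole totals 0-80 (BaP-EFL) and 0-72 (EPEC-BaP), with percentage = 100 × total / maximum. Recruitment bands from Table 1: green 50-72, amber 25-50, red <24, applied to counts 0-72.

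**Fidelity as printed, BaP-EFL (81 possible totals)**

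| Total | Percentage | Bands met | Number of totals |
|---|---|---|---|
| 0-47 | 0-58.8% | none | 48 |
| 48 | 60.0% | amber | 1 |
| 49-63 | 61.2-78.8% | amber and red | 15 |
| 64 | 80.0% | green, amber and red | 1 |
| 65-80 | 81.2-100% | green and red | 16 |

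Check: 48 + 1 + 15 + 1 + 16 = 81.

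**Fidelity as printed, EPEC-BaP (73 possible totals)**

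| Total | Percentage | Bands met | Number of totals |
|---|---|---|---|
| 0-43 | 0-59.7% | none | 44 |
| 44-57 | 61.1-79.2% | amber and red | 14 |
| 58-72 | 80.6-100% | green and red | 15 |

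Check: 44 + 14 + 15 = 73.

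The only total in either arm with a single rating is 48/80. A perfect score is both green and red, and a score of zero has no rating.

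**Fidelity with only the sign reversed (red <60%).** BaP-EFL: 0-47 red, 48-63 amber, 65-80 green, but 64/80 = 80% is still both green and amber. EPEC-BaP: 0-43 red, 44-57 amber, 58-72 green, with no overlap because 0.80 × 72 = 57.6 is not a whole total. Reversing the sign is therefore not enough; amber must also stop below 80%.

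**Recruitment as printed.** Counts 0-23 are red, 24 has no band, 25-49 are amber, 50 is green and amber, and 51-72 are green. If the amber endpoints are read as excluded, the overlap at 50 goes but both 24 and 25 have no band. Neither reading gives a complete partition.

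**Acceptability (TARS) row.** Amber is 55-74% and green is at least 75%. An unrounded proportion between 74% and 75% has no band. With assumed responder numbers (the SAP gives none), examples are 20/27 = 74.1% and 26/35 = 74.3%. Rounded to whole percentages, both are amber. The SAP states no rounding rule for these percentages.

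**Direction in the other rows.** The red bands for retention (<45%), SAPAS (<33%), recruitment (less than 24) and TARS (<55%) all run downwards. Fidelity is the only red band that points upwards.

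**The case against.** The strongest reply is that this is a one-character slip with only one plausible correction. The bands descend, the red label describes a failure of fidelity, and the other four red bands mean less than. No sensible analyst would declare 85% a failure, and no estimate, analysis or sample size depends on it. Fidelity and recruitment are also secondary progression parameters. The bands for the two primary ones, retention and SAPAS, are clean. Section 1.2 does not say that a single red row blocks progression, and an 85% result meets green as well as red, so the literal outcome is conflicting ratings and not a stop. The recruitment faults affect two single counts, and the TARS gap closes under whole-percent rounding.

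Much of this stands as to weight. The sign is very probably typographical, the consequence is best described as conflicting or absent ratings, and the recruitment and TARS points are minor. None of it makes the printed rule usable. Inferring the threshold is a decision that the SAP is meant to have made already, and the intended wording at 80%, 50 and 24 cannot all be read off the context. In particular, the text does not settle which side 24 belongs on. The protocol that the SAP supplements is not shown, so whether it carries the same text is unknown; the SAP needs correcting either way.

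**Conclusion.** The concern holds. The fidelity progression criterion is wrong as written: every result above 60% is red plus at least one other colour, and every result below 60% is unrated (48 of 81 BaP-EFL totals, 44 of 73 EPEC-BaP totals). Green and amber also share exactly 80%, which is attainable for BaP-EFL at 64/80. In the recruitment row, 50 has two ratings and 24 has none, taking 25-50 to include its ends.

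The need to correct this before data are seen rests on the fidelity row. The recruitment edges are minor. The TARS gap is minor too, and exists only if percentages are left unrounded. The conclusion assumes that the printed inequality is the SAP's own. This is likely, because the less-than signs in the other rows of the same table were read correctly.

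**What to change.** Rewrite the affected rows of Table 1 so that each possible result has exactly one rating:

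- **Fidelity:** (a) ≥80%; (b) ≥60% and <80%; (c) <60%.
- **Recruitment:** (a) 50-72; (b) 25-49; (c) 24 or fewer. This keeps the stated amber floor of 25. Amber 24-49 with red below 24 would be equally complete, so the sponsor should confirm where 24 belongs.
- **TARS:** (a) ≥75%; (b) ≥55% and <75%; (c) <55%. Alternatively, keep the present wording and state that percentages are rounded to whole numbers before rating.

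While the fidelity row is open, state which percentage is rated. Section 2.3 reports one for each group in each arm, whereas Table 1 names both programmes together.

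The cost is an SAP wording change, plus the matching protocol table if it carries the same text. No new data, analysis or sample size work follows. Date the change, and make it before fidelity and recruitment results are reviewed.

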### 1.3 Measures

#### Eligibility:

Interest form- where heard about the groups, borough.

Standardised assessment of Personality- Abbreviated scale (SAPAS)

#### Baseline Demographics.

We will collect parent & child age, sex, and ethnicity; family household composition and family socioeconomic status (including household income and previous education of both parents). We will also collect information about current mental health treatment and previous attendance to a parenting intervention.

#### Feasibility outcomes:

##### Recruitment and retention outcomes:

- (i) Proportion of participant identification (Number and percentage parents/caregivers who self-identify as interested in receiving BaP-Enjoying Family Life and participating in clinical trial)
- (ii) Proportion of trial participation:
  - a. Number and percentage of parents screened out of numbers interested,
  - b. Number and percentage of parents eligible from those consenting,
  - c. Number and percent of parents providing informed written consent from those interested
  - d. Number and percentage of parents randomisation from those eligible and consenting

and reasons for non-participation

- (iii) Number and proportion (percentage of total invited) of complete, partial complete and no response to questionnaire and observational assessments for data collection at baseline, Time 2 and 3 follow up in both arms of the trial and reasons for missing data. Retention for the feasibility progression parameter will be assessed based on proportion of completed primary outcome measure (i.e. child behaviour).

- (iv) Rates of intervention use:

- a. Uptake (Percentage of parents attending 1 session)
- b. Session attendance- mean and standard deviation number of sessions attended per arm
- c. Retention – number of treatment completers (attending 5 or more sessions), low attenders (number of parents attending 1-4 sessions), non-attenders.

from participants in both arms of trial and reasons for missed sessions and drop out

##### Intervention and trial acceptability outcomes

- (v) Treatment acceptability and group experience: Treatment Acceptability Rating Scale (TARS), Group Cohesiveness Scale (GCS; Wongpakaran et al., 2013), only collected at T2.
- (vi) Treatment Fidelity: a specially designed weekly fidelity measure containing 4 items and completed by parent group leaders together after each session.

- (vii) Nested process evaluation: Key informant semi-structured interviews will be conducted with parent/caregiver participants in order to explore treatment acceptability, implementation of trial procedures and intervention delivery.

### **Clinical outcomes:**

#### Primary outcome:

- (i) Child behaviour: Eyberg Child Behaviours Inventory (Eyberg et al., 1978); Concerns About My Child (CAMC; Scott et al., 2001; Day et al., 2017)

#### Secondary outcomes:

- (ii) Parenting behaviour: Arnold O’Leary Parenting Scale (Arnold et al., 1993)
- (iii) Parent-child observational assessment: Home Observation Measurement of the Environment (Department of Health, Cox and Bentovim., 2000)
- (iv) Parenting satisfaction and self-efficacy: Kansas Parental Satisfaction Scale (KPSS; James et al., 1985), Brief Parent Self Efficacy Scale (National academy of Parenting Research)
- (v) Parent wellbeing: Brief adjustment Scale- 6 (BASE-6; Cruz et al., 2019)
- (vi) Parent reflective function: Parent reflective function questionnaire (Luyten et al., 2017)

